7.2 Safety Laboratory Measurements

This study has no safety laboratory measurements.

7.3 Data and Safety Monitoring Board

An independent Data and Safety Monitoring Board (DSMB) will be set up for periodic review of safety data during the study conduct. The composition and responsibilities of DSMB members (Medical Monitoring/ audit team) are presented in Table 1 and section 9.3, respectively.

7.4 Study pause

Pause rules will pause or halt further treatment and participants already enrolled will continued to be followed for safety during the pause. The study will be paused if there are any suspected adverse reactions where 1 or more participants experience any treatment-related Grade 4 AE or SAE.

8. STATISTICAL CONSIDERATIONS AND ANALYSIS PLAN

8.1 Sample size calculations

As a pilot study, we will recruit 8 asymptomatic plasmodium carriers per study-arm in the 6 trial arms and 4 participants per arm in the 2 control (placebo) arms. Therefore 56 positive participants will be enrolled per site, making 112 participants in the whole study. To reach the required number of 56 gametocyte carriers, 635 persons will be RDT tested in Buea (south west region) where the expected positive RDT was 9.8% in Demographic health survey (DHS) 2018 (34) and drop-out rate was set at 10%. In Huye (South region) where the expected positive RDT was 6.9% in Malaria indicator survey (MIS) 2017 (35) and drop-out rate was set at 10%, 432 persons will be RDT tested to reach the required number of 56 gametocyte carriers.

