designs, potential gain, and their right to stop at any moment if they accept to enter the study. Then they will be requested to sign a written informed consent. Number of study Fifty-six positive participants have to be enrolled per site, making 112 participants in the whole participants: study. To reach the required number of gametocyte carriers, 635 persons will be RDT tested in Buea (Southwest region) where the expected positive RDT was 9.8.% in Demographic health survey (DHS) 2018 and drop-out rate was set at 10%. In Huye (South region), the expected positive RDT was 14.4% in Malaria indicator survey (MIS)2017 and drop-out rate was set at 10%, hence 432 persons will be RDT tested to reach the required number of gametocyte carriers. Study All students and staff members of the University will be invited to participate in the study. population Participants will be included in the study if in good health (based on physical examination and /Participants medical history), and if they meet all specified eligibility criteria. characteristics/ Inclusion criteria for trial allocation groups Study sites/ Asymptomatic Plasmodium positive students or workers from the selected study universities, aged 18 years and above who provide written informed consent. **Exclusion criteria for trial allocation groups** 1. To have a known hypersensitivity to any ingredients of the tea. 2. Currently taking any malaria drug for prevention or treatment. 3. To have participated in another malaria drug trial or device in the last 1month. 4. To have a history or presence of clinically significant medical, psychiatric, or emotional condition. The study will be conducted at the University of Buea in Cameroon, and the University of Rwanda. All students and staff members of the University will be invited to participate. In the University of Buea, there are about 12,000 students and 973 staff members (500 teachers and 473 administrative /supporting staff. The University of Rwanda (UR), has about 30,445 students and 2,266 staff members (1450 teachers and 816 administrative /supporting) Composition of The study treatments (Artemisia Afra) and control (placebo) will be prepared in the various study and formulations as follows: control Artemisia afra available as infusions containing 5g of Artemisia per liter, will be prepared by adding treatments 5 g dried leaves and twigs of A. afra (in a tea sachet / tea bag) to 1 liter of boiling water, infused for 10 min, and filtered through a sterilized 1 mm mesh. Artemisia afra available as infusions containing 5g of Artemisia in per 500ml, will be prepared by adding 5 g dried leaves and twigs of A. afra (in a tea sachet / tea bag) to 500ml of boiling water, infused for 10 min, and filtered through a sterilized 1 mm mesh. Flavored Artemisia afra available as infusions containing 5g of flavored Artemisia per liter, will be prepared by adding 5 g of flavored dried leaves and twigs of A. afra (in a tea sachet / tea bag) to 1 liter of boiling water, infused for 10 min, and filtered through a sterilized 1 mm mesh. Flavored Artemisia afra available as infusions containing 5g of flavored Artemisia per 500ml, will be prepared by adding 5 g of flavored dried leaves and twigs of A. afra (in a tea sachet / tea bag) to 500mls of boiling water, infused for 10 min, and filtered through a sterilized 1 mm mesh. Flavored placebo available as infusions containing flavored inactive substance per liter, will be prepared by adding flavored inactive substance (in a tea sachet / tea bag) to 1 liter of boiling water, infused for 10 min, and filtered through a sterilized 1 mm mesh. Regular tea placebo will be any tea of choice routinely taken by the selected participants. After preparation, the following doses will be obtained for consumption by participants with

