Rapid diagnostic test (RDT), Positive (Pos) Negative (Neg), Real time Polymerase Chain reaction (rt-PCR), Quantitative Polymerase Chain reaction (qPCR)

[figure not shown]

Figure 3. Algorithm to find the activity level, optimal dosage, and accepted formulation of *Artemisia afra* in eliminating plasmodium reservoirs.

Study description:

Study population: The trial will be conducted among Plasmodium infected asymptomatic students and workers in the University of Buea -Cameroon and the Rwanada National University (UR. Fifty-six positive participants have to be enrolled per site, making 112 participants in the whole study. To reach the required number of gametocyte carriers, 635 persons will be RDT tested in Buea (South-west region) where the expected positive RDT was 9.8% in Demographic health survey (DHS) 2018 (34) and drop-

out rate was set at 10%. In Kigali where the expected positive RDT was 14.4% in Malaria indicator survey (MIS)2017 (35) and drop-out rate was set at 10%, hence 432 persons will be RDT tested to reach the required number of gametocyte carriers.

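### Section 8.1 gives 6.9% expected RDT positivity for the Rwanda site, but its 432 tests follow only from the 14.4% stated in the synopsis and section 3

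*Protocol*

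**What the plan says.** The protocol gives the Rwanda screening number in three places.

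- **Section 8.1 (sample size):** "In Huye (South region) where the expected positive RDT was 6.9% in Malaria indicator survey (MIS) 2017 (35"), and then "432 persons will be RDT tested to reach the required number of 56 gametocyte carriers".
- **Synopsis, number of study participants:** "In Huye (South region), the expected positive RDT was 14.4% in Malaria indicator survey (MIS)2017", again with 10% drop-out and 432 tests.
- **Section 3, study population:** "In Kigali where the expected positive RDT was 14.4% in Malaria indicator survey (MIS)2017 (35"), again with 10% drop-out and 432 tests.

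The enrolment target is the same throughout. Section 8.1 puts it as "Therefore 56 positive participants will be enrolled per site, making 112 participants in the whole study". For Cameroon all three places agree: 9.8% positivity, 10% drop-out and 635 tests.

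**The concern.** One survey is credited with two positivity rates for Huye, 6.9% and 14.4%. The 14.4% is also attached to two different places, Huye and Kigali. The screening number stays at 432 although it depends directly on the rate. The two rates differ by a factor of about two (14.4/6.9 = 2.1), so they cannot both lead to 432.

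The sample size section is where a reader would check the number, and there it cannot be reproduced from its own inputs. The practical stake is planning at one of two sites. If 6.9% is the right rate, test kits, budget and screening time in Rwanda have been set at less than half of what the target needs.

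**Working it through.** **Inputs, all from the protocol**
- Target per site: 6 × 8 + 2 × 4 = 56 (section 8.1).
- Drop-out: 10% (all three places).
- Buea: 9.8% positivity, 635 tests (all three places).
- Rwanda: 6.9% (section 8.1) or 14.4% (synopsis, section 3); 432 tests (all three places).

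**Step 1: recover the formula from Buea.** With tests = 56 / p / (1 − 0.10):
56 / 0.098 / 0.9 = 634.9. The protocol says 635, so this is its formula.

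**Step 2: apply it to Rwanda.**
- p = 14.4%: 56 / 0.144 / 0.9 = 432.1, the stated 432.
- p = 6.9%: 56 / 0.069 / 0.9 = 901.8, so 902, which is 902 − 432 = 470 more than stated.
- Rate implied by 432: 56 / 432 / 0.9 = 14.4%.

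**Step 3: could another drop-out convention give 432 at 6.9%?**

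| Convention | Tests at 6.9% |
|---|---|
| 56 / 0.9 / p | 901.8 |
| 56 × 1.1 / p | 892.8 |
| 56 / 0.9 rounded up to 63, then / p | 913.0 |
| 56 × 1.1 rounded up to 62, then / p | 898.6 |
| no drop-out allowance, 56 / p | 811.6 |

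None comes near 432, so neither rounding nor the choice of formula explains the gap.

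**Step 4: expected yield of 432 tests.**
- At 14.4%: 432 × 0.144 = 62.2 RDT positives; × 0.9 = 56.0.
- At 6.9%: 432 × 0.069 = 29.8 RDT positives (53% of 56); × 0.9 = 26.8 (48% of 56).

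Under a binomial model, the chance of at least 56 RDT positives among 432 at 6.9%, before any drop-out, is about 5 in a million. None of these figures allows for RDT positives later excluded as qPCR negative (section 5.7), because the protocol's formula does not.

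**Step 5: study total.** Planned screening is 635 + 432 = 1067. At 6.9% for Rwanda it would be 635 + 902 = 1537.

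**The case against.** The best defence is that 432 is the sound number and 6.9% a stray figure. Two of the three places give 14.4%, all three give 432, and the formula that yields 635 for Buea yields 432 at 14.4%. That is a plausible reading, and it means 432 should not be called wrong outright. It does not remove the contradiction. The 6.9% stands in the current text of the sample size section, and without the cited survey it cannot be dismissed. The change of place name adds to the doubt, since the rate may depend on the district.

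A reader might infer that the Rwanda site will end with about half its participants: 27 instead of 56, roughly 4 per active arm (26.8 × 2/14 = 3.8) and 2 per control arm (26.8 / 14 = 1.9), and 56 + 27 = 83 of 112 overall. The documents do not support that. It needs 6.9% to be right and screening to stop at 432. The protocol fixes enrolment at 56 per site, presents 432 as the means to reach it, and nowhere ends screening there. All students and staff are invited, and the University of Rwanda has about 30,445 + 2,266 = 32,711 of them, so 902 would be under 3% of the pool. The documented consequence of a 6.9% rate is more screening.

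Two smaller limits also stand. The yield falls below half of 56 only after the 10% drop-out is removed; before that it is 53%. And 432.1 written as 432 rather than 433 is rounding, not an error.

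It can also be said that this is a pilot without a formal sample size calculation, so the screening number feeds no power statement, and the 56 does not depend on positivity. That is correct and lowers the severity.

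**Conclusion.** The protocol contradicts itself on the expected positivity at the Rwanda site, and section 8.1 pairs a rate with a screening number that does not follow from it. Under the protocol's own formula, 432 belongs to 14.4%, and 6.9% requires about 902. Which rate is right cannot be settled from the document.

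The consequence is therefore conditional. If 14.4% applies, the plan is intact apart from a wrong percentage in 8.1. If 6.9% applies, screening is under-planned by 470 tests, and the planned 432 would be expected to give about 30 RDT positives, or about 27 after drop-out, against 56. This rests on the 10% drop-out and on every RDT positive being confirmed, as the formula assumes. Severity: should-fix.

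**What to change.** Look up the cited 2017 survey for the district where recruitment will take place. Then state one site (Huye or Kigali) and one positivity in the synopsis, section 3 and section 8.1, and do one of the following:

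- If 14.4% is confirmed, correct 6.9% to 14.4% in section 8.1 and keep 432.
- If 6.9% is confirmed, state it in all three places and change 432 to about 902 in each.

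If the survey gives another rate for that district, recompute with 56 / p / 0.9.

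In the first case the cost is one source check, one corrected percentage and a consistent place name. In the second it is edits in three places plus kits and staff time for about 470 more tests. The target of 56, the arm sizes and the allocation do not change. The check is best made before kits are ordered for the Rwanda site.

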8.2 Analysis Populations

- **8.2.1 Enrolled Population:** All screened participants who provide informed consent and receive a participant ID, regardless of the participant's randomization and treatment status in the trial.
- **8.2.2 Exposed Population:** All participants in the enrolled population who receive a treatment dose.
- **8.2.3 Trial Populations:** Treatment trial analyses will be performed on both the Full Analysis (FA) Population and Per Protocol (PP) Population.

Full Analysis Population: All participants in the enrolled population who were randomized, received a study treatment dose, and provided an evaluable blood sample at least at one time point post-treatment. Per Protocol Population: All participants in the FA Population who correctly received all doses of study treatment per randomization with no major protocol violations that are determined to potentially interfere with the reactivity assessment of the study treatment. This population will serve as the primary analysis population for all efficacy objectives. Due to unpredictability of some irregularities, the criteria for exclusion of participants from the Per Protocol Population will be determined before the database is locked and will be based on the blind review of protocol violations.

8.2.4 Safety Population

All participants in the enrolled population who received a study treatment and had any safety data available.

Participants will be analyzed as "treated" (i.e., according to the actual treatment received). All safety analyses will be performed using this population. The denominators for different safety endpoints may vary according to the number of participants with available data for the specific endpoint.

8.3 Analysis Plan

➤ Data management and analysis: All data will be entered into an Excel spreadsheet and then analyzed STATA 17 software packages. Descriptive statistics will be used to redistribute the treatment outcomes in the various treatment arms according to the evaluation times.

Quantitative variables will be summarized using means and medians followed by their standard deviations (SD) and Interquartile range (IQR) respectively, while qualitative variables will be summarized as percentages. Groups will be compared using a linear mixed model and trends over time will be compared using F-tests at 95% CI and statistical significance set at P < 0.05.

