2.3.2 Secondary objectives

- 1. To assess participants response (treatment efficacy) to varying dose concentrations, dose frequency, length of treatment, and formulation of *Artemisia afra* treatment.
- 2. To identify the most acceptable dose concentration, dose frequency, length of treatment, and formulation (flavor) of Artemisia treatment.
- 3. To assess the safety (ASE) of *Artemisia afra* treatment in participants by dose concentration, dose frequency, length of treatment, and formulation. As a commonly used tea, no toxicity is expected.
- 4. To assess variability of plasmodium test predictive values between mRDT, rtPCR, and direct blood smear observation in asymptomatic persons.

Treatment outcomes

Major outcome

• Decrease in parasite load over time.

Secondary outcomes

- Decrease in gametocyte load in carriers with Artemisia afra tea by dose concentration, dose frequency, length of treatment, and formulation.
- Acceptability (adherence and completion) of *Artemisia afra* treatment by dose concentration, dose frequency, length of treatment, and formulation (flavor).

- Safety (SAEs) of *Artemisia afra* treatment in participants by dose concentration, dose frequency length of treatment, and treatment formulation.
- Absolute increase in Cycle threshold (Ct >20).
- Likelihood and variability in the rate of reservoir elimination with treatment, compliance/ acceptability, and occurrence of side effects /adverse events in different treatment arms.

Treatment endpoints

Primary endpoints

• Proportion of people with decreased gametocyte load after treatment with *Artemisia afra* tea on Day 35 from baseline.

Secondary endpoints

- Level of decrease in gametocyte load (rt-PCR Ct) in the different treatment arms at D7, D14, D28, and D35 from baseline (activity level and optimal dosage schedule).
- Level of decrease in gametocyte load the various treatment arms (rt-PCR Ct) by gender, age, and trial entry parasite load, at D7, D14, D28, and D35 from baseline.
- Absolute increase in Cycle threshold (Ct >20) in various treatment arms at D7, D14, D28, and D35 from baseline.
- Proportion of people in the various treatment arms who respect and complete the prescribed treatment dosages (accepted dosage schedule and drug formulation).
- Proportion of persons on the various arms of treatment who develop clinical symptoms at D7, D14,
 D28, and D35 from baseline.

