3. METHODOLOGY

Study Design: The study is a Phase 2 randomized controlled, partial-blind, parallel group study in plasmodium infected *asymptomatic* adults 18 years and older, with 8 study arms. It will use the adapted Zelen design. The adapted Zelen design uses two steps in the consent process. In the first step, there is an informed consent from all participants for a cohort lifestyle study. After consent is obtained, baseline assessment and screening will be performed, and eligible participants randomly assigned to the different study arms. According to this consent, participants are randomized without knowledge about the detailed protocol. In the second step, only participants from the intervention group will receive the information about the intervention and the second consent will be obtained from them. The participants who will decline to participate to an intervention will continue in the cohort study, as the control group.

Duration of study: The study duration is 35 days (5 weeks) for each participant.

Treatment groups (TG):

TG 1: Group of 8 persons receiving *A. afra* infusions of 5g/1liter of water, 3drinks a day, daily for 1week (7 days) (current recommendation).

TG 2: Group of 8 persons receiving *A. afra* infusions of 5g/500ml of water, 2drinks a day, daily for 1week (7 days) (increase concentration and decrease dose frequency).

TG 3: Group of 8 persons receiving *A. afra* infusions,5g/1liter of water 3drinks a day, weekly for 4weeks (decrease dose frequency and increase length of treatment).

TG 4: Group of 8 persons receiving flavored *A. afra* infusions, 5g/1liter of water 3drinks a day, daily for1week (7 days) (current treatment with improved taste).

TG 5: Group of 8 persons flavored *A. afra* infusions, 5g/500ml of water 2drinks a day, daily for 1 week (7 days) (improved taste, increase concentration and decrease dose frequency).

- **TG 6:** Group of 8 persons receiving flavored *A. afra* infusions, 5g/1liter of water 3drinks a day, weekly for 4weeks (improved taste, decrease dose frequency and increase length of treatment);
- **TG 7**: Group of 4 persons receiving flavored placebo infusions, 5g/liter of water 3drinks a day, daily for 1week (7 days) (improved taste with no active molecule);
- **TG 8**: Group of 4 participants receiving regular tea placebo taken as desired, daily for 1 week (7 days) (Regular tea with no active molecule).

[figure not shown]

Figure 2. Screening and recruitment of study participants

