Randomization: Prior to treatment, eligible participants will be randomly assigned into the 8 study arms. The randomization method will be a permuted block randomization, with a block size of either 14 or 28 at random, and with a two-to-one allocation ratio for each active arm against two different control arms (2:2:2:2:2:1:1).

Blinding: The participants in the intervention arms will be aware of their assignment to an intervention group but unaware of the treatment assigned to them. The site staff (investigators or observers) will be

aware of assignments to one control arm (regular tea group), but unaware of assignments in the other treatment arms.

Visits/assessment schedules: A total of five study visits will be effected, being one baseline visit on Day 0, and four follow-up visits on Day 7, 14, 28 and 35, from baseline. During the baseline visit plasmodium tests targeting specific parts of the gametocyte genes will be done to determine the participants' initial (baseline) parasite load, and during subsequent visits, follow up control tests (rtPCR and blood smear) will be done, and the gametocyte load recorded, alongside assessments for clinical symptoms and adverse sides effects (if any).

Endpoints The efficacy of each of the treatment dosage schedule will be evaluated on day 7,14,28 and 35 from baseline, based on response to treatment or reservoir elimination rate. Response to treatment will be indicated by an absolute increase in Cycle threshold (Ct >20), or a negative rt-PCR tests results (Ct >40). If the patient misses the follow-up visit, compliance will be noted in the completion worksheet (filled out at end of study) and the parasite load and adverse side effects noted during the last visit considered. No severe side adverse effects are expected from the treatment but since toxicity is always a concern in clinical trials involving humans, participants will be observed for any severe ASEs and withdrawal noted throughout the study duration.

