The site staff should complete the eCRFs as soon as possible after the information is collected. Completed eCRFs must be submitted for each screened participant who signs the study specific informed consent form. The study coordinator/sponsor is responsible for data management activities, including quality review, analysis, and reporting of the study data according to the SOPs. Internal data quality checks such as automatic range checks, checks to identify data that appear inconsistent, incomplete, or inaccurate are programmed into eCRF that does real time review of the data as and when clinical data is entered into the system by the site staff. The Data Management team will review the data for quality and will provide several quality assurances reports to ensure that study data are clean and complete. Quality assurance reports will include, but are not limited to, the following: missing forms, missing values and out of range values, automated data queries, and manual review of study data. Data queries will be distributed to the sites at scheduled time periods for the site staff to review and update the database.

Coding: All medical verbatim terms will be coded by a medical doctor according to MedDRA (adverse events, medical history, and concomitant diseases) (39) and the WHO Drug Dictionary enhanced version (concomitant medication) (40).

Database Lock Procedures

Database will be locked upon completion of the following activities:
☐ All participants have completed the follow up visits
☐ All the participants data have been entered in the database
☐ All data anomalies have been resolved
☐ Study monitoring has been completed
☐ All the listings of the database have been reviewed and discussed for assessment of consistency and
medical plausibility.
Procedures for Analysis
The data will be analyzed after the database lock, as per the pre-specified Statistical Analysis Plan (SAP)
in section 8.2 and 8.3 above. An audit trail will be kept of all subsequent changes to the data.

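### Section 8.3 tests arms by an undefined time trend and states no Day 35 contrast, although the primary endpoint is at Day 35 and regimens run over 1 or 4 weeks

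*Protocol*

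**What the plan says.** Section 8.3 compares arms as follows: "Groups will be compared using a linear mixed model and trends over time will be compared using F-tests at 95% CI", with "statistical significance set at P < 0.05". Qualitative variables are to be summarised as percentages, and no between-arm comparison is named for them. Section 9.4 identifies the pre-specified statistical analysis plan as standing "in section 8.2 and 8.3 above", so the protocol presents this sentence as the plan itself.

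The primary endpoint, under Treatment endpoints, is "Proportion of people with decreased gametocyte load after treatment with" the study tea, at Day 35 from baseline. The first secondary endpoint is "Level of decrease in gametocyte load (rt-PCR Ct) in the different treatment arms at D7, D14, D28, and D35 from baseline". Section 3 sets "one baseline visit on Day 0, and four follow-up visits on Day 7, 14, 28 and 35, from baseline".

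Section 3 also sets two treatment lengths. TG1 is dosed "daily for 1week (7 days) (current recommendation", and TG2, TG4 and TG5 also run for 7 days. TG3 is "3drinks a day, weekly for 4weeks (decrease dose frequency and increase length of treatment", and TG6 follows the same calendar. The primary objective is to find the optimal concentration, frequency, length of treatment and flavour.

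**The concern.** The trial has to choose between regimens, and its primary time point is Day 35. The inference in 8.3 rests on a comparison of trends, and a trend mixes when the load falls with how far it has fallen by Day 35. Exposure differs by design. At the Day 7 visit a TG1 participant has had all 3 × 7 = 21 planned drinks, while a TG3 participant has had 3 or 6 of 3 × 4 = 12, depending on whether the second weekly dose precedes the visit. Response curves of different shape can therefore be expected.

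Because time is not defined, two analysts could follow 8.3 faithfully and reach different conclusions, neither of them about Day 35. The choice of regimen could then depend on the speed or curvature of the response when the endpoint asks about its level at the end.

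**Working it through.** **Arm sizes.** Section 8.1 gives 8 per active arm and 4 per control arm at each of two sites: 2 × (6×8 + 2×4) = 112, which agrees with the protocol. Over both sites this is 16 per active arm and 8 per control arm.

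**Assumptions.** The protocol gives no Ct curve, SD or effect size. Assumed mean rises in Ct (a rise means a lower load) at Days 0, 7, 14, 28 and 35 are:
- early plateau: 0, 8, 8, 8, 8
- gradual: 0, 2, 4, 8, 8
- rebound: 0, 8, 6, 4, 3
- control: 0 throughout

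SD is 3 to 6 Ct and within-person correlation is 0.5.

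**Slopes.** Slope = Σ(t − t̄)y / Sxx, with t̄ = 16.8 and Sxx = 842.8.
- Plateau: 134.4 / 842.8 = 0.159 per day
- Gradual: 204.4 / 842.8 = 0.243 per day, 52% steeper with the same Day 35 value
- Gradual reaching only +6 (0, 1.5, 3, 6, 6): 153.3 / 842.8 = 0.182 per day, still steeper than the plateau arm at +8
- Rebound: 4.2 / 842.8 = 0.005 per day, close to control

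The mean post-baseline level orders plateau and gradual the other way: 8.0 v 5.5. A group term and a slope in the same model can therefore point in opposite directions.

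**Rejection rates.** Let d be the difference between two arm curves, m = n₁n₂/(n₁+n₂), N = n₁+n₂ and s² = SD²(1 − 0.5). Noncentrality (noncentral F, 5% level) is:
- linear slope (1 and 4(N−2) df): m[Σ(t − t̄)d]² / (Sxx·s²)
- arm-by-visit (4 and 4(N−2) df): mΣ(d − d̄)² / s²
- change to Day 35 (1 and N−2 df): m·d₃₅² / (2s²)

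Gradual v plateau, 16 v 16, so m = 8. At SD 5, s² = 12.5:
- slope: 8 × 70² / (842.8 × 12.5) = 3.72
- arm-by-visit: 8 × 32 / 12.5 = 20.5
- Day 35: 0

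| SD | Linear slope | Arm-by-visit | Day 35 change |
|---|---|---|---|
| 3 | 89% | 100% | 5% |
| 5 | 48% | 96% | 5% |
| 6 | 36% | 86% | 5% |

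The Day 35 values are equal, so only the Day 35 contrast stays at its nominal level.

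Rebound v control, 16 v 8, SD 5, so m = 5.33:
- linear slope: 5%
- Day 35 change: 5.33 × 9 / 25 = 1.92, giving 26%
- arm-by-visit: 5.33 × 36.8 / 12.5 = 15.7, giving 89%
- mean post-baseline change: 5.33 × 5.25² / (12.5 × 1.25) = 9.4, giving 83%

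Rebound v sustained plateau, 16 v 16, SD 5: the linear slope separates the arms in 94% of trials.

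**The case against.** A linear mixed model need not be linear in time. With five fixed visits, treating visit as a factor is at least as natural, and on that reading three stronger inferences fail.

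- A reader might infer that the test favours slow regimens by construction. An overall F-test ranks nothing. A ranking arises only if someone orders arms by estimated linear slopes, and 8.3 does not say that anyone will.
- A reader might infer that a rebounding arm is missed. That holds only for a linear slope against control. The arm-by-visit test has 89% power in the same example, and even the slope separates the rebound from a sustained arm.
- A reader might infer that the different dosing calendars make the interaction significant. They need not. With the assumed curves scaled to a 3-cycle gain, the arm-by-visit test over the six active arms rejects in 29% of trials at SD 5 and 20% at SD 6. The literature review also notes that gametocytes often outlast successful therapy, so an early fall in the 7-day arms is not established.

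The time course is also a stated target. The major outcome is the fall in parasite load across time, and section 3 evaluates efficacy at all four follow-up visits. The group comparison is a separate clause that could carry a level contrast.

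All of this stands, and it rules out dropping the time test. What it does not supply is a Day 35 comparison. None is stated in 8.3, and the synopsis names a Cox regression for time to elimination, which is not one either.

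**Conclusion.** The point holds in a limited form. Section 8.3, which the protocol calls its analysis plan, ties inference to an undefined trend and states no Day 35 contrast, while the primary endpoint is at Day 35 and treatment length differs by design.

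If time is linear, a slower regimen can show a steeper slope than a faster one with the same, or even a better, Day 35 result, and an arm that falls and then rebounds can look like control. If time is categorical, the test can be significant when Day 35 results are equal, and it gives no ranking. On the assumed curves, with equal Day 35 values, rejection runs from 36% to 89% on the first reading and from 86% to 100% on the second.

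These sizes are illustrative and depend on the curves, SDs and correlation chosen. The mismatch between the stated test and the Day 35 endpoint does not depend on them.

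**What to change.** In section 8.3:
1. Enter visit in the mixed model as a five-level factor (Days 0, 7, 14, 28, 35).
2. Compare the Day 35 proportion with decreased load between arms as the primary endpoint analysis. A difference in mean Ct does not by itself analyse that proportion.
3. State the model-based arm difference at Day 35, with its 95% CI, as the main comparison for level of decrease.
4. Report the Day 7, 14 and 28 contrasts, and keep the arm-by-visit F-test as supportive evidence on the time course.
5. State that regimens are not chosen by a linear slope.

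The cost is analysis wording only: no visit, sample or participant changes. The downside is that the Day 35 contrast has less power than a test over all visits to show transient activity (about 26% v 89% in the assumed rebound example), which is why the supportive test should stay.
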